7.1 Primary Endpoints

For each study endpoint defined below, we include the cohort in which it is assessed.

Primary Endpoint 1 (MITT Cohort): Vaccine efficacy

HIV-1 infection diagnosed after enrollment (concurrent with first vaccination) through the Month 24 visit

Primary Endpoint 2 (Safety Cohort): Vaccine safety

Number and frequency of:

- Local reactogenicity signs and symptoms occurring within 3 days after each vaccine/placebo dose
- Systemic reactogenicity signs and symptoms occurring within 3 days after each vaccine/placebo dose
- Adverse events by body system, Medical Dictionary for Regulatory Activities (MedDRA) Preferred Term, severity, and assessed relationship to study products within 30 days after each vaccine/placebo dose
- SAEs, AEs of special interest (AESIs), and new chronic medical conditions (defined as a new onset or exacerbation of medical condition requiring 2 or more visits to a medical provider during a period of at least 30 days) occurring at any time throughout the study
- AEs leading to early participant withdrawal or early discontinuation of study product(s) administration throughout the study

7.2 Secondary Endpoints

Secondary Endpoint 1 (MITT Cohort): Durability of VE

HIV-1 infection diagnosed after enrollment through 36 months post enrollment

Secondary Endpoint 2 (Week 26 At-Risk Cohort): Week 26+ VE

HIV-1 infection diagnosed after Month 6.5 through 24 months post enrollment

Secondary Endpoint 3 (Immunogenicity Cohort): Immunogenicity

Immune responses at Month 6.5 (Week 26 visit) from assays based on the HVTN Laboratory Assay Algorithm such as vaccine-specific binding antibodies and T cell responses. The primary time-point for immunogenicity assessment is the Week 26/Month 6.5 visit, 2 weeks after the Month 6 vaccination. Immunogenicity assessments will also be performed at the Month 0, 12.5, 18, 18.5, and 24 visits (the ‘immunogenicity time-points’ for measuring immune responses; see protocol Appendix F).

Secondary Endpoint 4 (Immunogenicity Cohort): Correlates of Risk

Immune responses from assays based on the HVTN Laboratory Assay Algorithm (available at <https://atlas.scharp.org/>) and/or more assays down-selected from a larger pool of pilot studies, in HIV-1-infected vaccine cases and HIV-1-uninfected vaccine controls.

Secondary Endpoint 5 (MITT Cohort): VE by demographics, including sex at birth

HIV-1 infection diagnosed after enrollment through Month 24, and through Month 36 if Stage 2 occurs, by demographic characteristics including sex at birth

Secondary Endpoint 6 (MITT Cohort): VE by HIV genotype

HIV-1 infection diagnosed after enrollment through Month 24, and through Month 36 if Stage 2 occurs, and genotypic characteristics of viral sequences from HIV-1-infected participants at first evidence of HIV-1 infection, such as signature site mutations.

Full genome HIV-1 sequences will be measured from each subject in the MITT Infected Cohort. Five sequences will be measured at the EPIT (earliest post-infection time-point, based on the ‘look-back’ procedure) and 5 sequences will be measured at a later visit selected to be between 3 and 6 months after the EPIT.

Secondary Endpoint 7 (MITT Infected Cohort): Sieve analysis

Viral sequences from HIV-1-infected participants at the EPIT

7.3 Exploratory Endpoints

This section lists endpoints for several key exploratory objectives.

Exploratory Endpoint 1 (MITT Infected Cohort): Vaccine effect on post-infection endpoints

Viral load (VL) at the time of HIV-1 infection diagnosis, and VL and CD4+ T cell count within 6 months PD

VL and CD4+ values measured after ART initiation will be censored at the time of ART initiation, because ART will typically have a strong effect on these biomarkers. VL values that are left- or right-censored by the quantification limits (40 to 10,000,000) of the primary

VL assay will be assigned value $\log_{10}(20)$, and right-censored values will be assigned a value $\log_{10}(10,000,000) = 7$.

Exploratory Endpoint 2 (Immunogenicity Cohort): Exploratory immunogenicity

Endpoints for additional immunogenicity assays performed on samples from immunogenicity timepoints, based on the HVTN Laboratory Assay Algorithm.

Exploratory Endpoint 3 (MITT Population): Host genetics

Host genetic factors including HLA alleles and KIR genes measured in the Immunogenicity Cohort

8 General Approach to Handling Missing Data

All primary analyses will assume missing data are missing completely at random (MCAR), i.e., that whether a data point is missing does not depend on any observed or unobserved data. When missingness is negligible, statistical methods based on the MCAR assumption can be used with limited impact on the analysis. We will assess the MCAR assumption in terms of whether subject characteristics are associated with time-to-event outcome (e.g., dropout) using the Cox regression model or with longitudinal binary outcome (e.g., missed visits) using logistic generalized estimating equation (GEE) models. When the frequency of missing data is more substantial, methods that require the MCAR assumption may give misleading results. In this situation, statistical analyses will be performed with methods such as targeted minimum loss-based estimation (TMLE) for cumulative incidence estimation, use of auxiliary covariates for the hazard ratio estimate (Lu and Tsiatis, 2008, *Biometrika*), covariate adjustment, weighting methods, or combined with imputation, under the assumption that the missing data are missing at random (MAR). MAR assumes that the probability of an observation being missing only depends on the observed responses or covariates. Thus, this assumption is less stringent than the MCAR assumption. We will consider including any of the available baseline predictors of the missing outcomes as covariates or auxiliary variables in statistical models.

9 Statistical Analysis of Safety

Safety endpoints will be assessed in the Safety Cohort. All analyses will only use samples and data gathered prior to study unblinding.

Reactogenicity The number and percentage of participants experiencing each type of reactogenicity sign or symptom will be tabulated by severity. For a given sign or symptom, each participant's reactogenicity will be counted once under the maximum severity for all injection visits. In addition to the individual signs or symptoms, the maximum severity of local

pain or tenderness, induration, or erythema, and of systemic symptoms will be calculated. Kruskal-Wallis tests will be used to test for differences in severity between the vaccine and placebo groups at the final analysis of reactogenicity.

Adverse experiences Adverse experiences (AE) will be analyzed using MedDRA preferred terms. The number and percentage of participants experiencing each specific adverse experience will be tabulated by severity and by relationship to treatment. For the calculations in these tables, each participant's adverse experience will be counted once under the maximum severity or the strongest recorded causal relationship to study product.

A listing of SAEs reported to the DAIDS Regulatory Support Center (RSC) Safety Office will provide details of the events including severity, relationship to study product, time between onset and last vaccination, and number of vaccinations received.

A listing of AESIs will provide details on severity, date of onset, relationship to study product, number of vaccinations received and days since last vaccination.

A listing of new chronic medical conditions (defined as a new onset or exacerbation of medical condition requiring 2 or more visits to a medical provider during a period of at least 30 days) occurring at any time throughout the study will be provided.

Reasons for discontinuation of vaccinations and early study termination The number (percentage) of participants who discontinue vaccinations and who terminate the study early will be tabulated by reason (including AEs leading to early participant withdrawal or early discontinuation of study product(s) administration throughout the study) and treatment arm.

Formal comparisons of reactogenicity and AE between treatment arms at final analysis To determine whether there are significantly different rates of safety endpoints between the vaccine and placebo groups, we will evaluate four aggregate endpoints based on the Barnard's exact test. These aggregate endpoints are the rate of any reactogenicity, the rate of any related adverse event, the rate of any reactogenicity of grade 3 or higher, and the rate of any related adverse event of grade 3 or higher.

See the Appendix for a complete list of the DSMB safety report tables and figures.

10 Statistical Analysis of Biological Efficacy, Activity and Clinical Endpoints

Except where specified, all vaccine activity and efficacy endpoints will be evaluated in the MITT cohort. All analyses will only use samples and data gathered prior to study unblinding.

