PROTOCOL

HVTN 702

A pivotal phase 2b/3 multi-site, randomized, doubleblind, placebo-controlled clinical trial to evaluate the safety and efficacy of ALVAC-HIV (vCP2438) and Bivalent Subtype C gp120/MF59 in preventing HIV-1 infection in adults in South Africa

DAIDS DOCUMENT ID 12059

CLINICAL TRIAL SPONSORED BY

Division of AIDS (DAIDS) National Institute of Allergy and Infectious Diseases (NIAID) National Institutes of Health (NIH) Department of Health and Human Services (DHHS) Bethesda, Maryland, USA

STUDY PRODUCT(S) PROVIDED BY

Sanofi Pasteur Swiftwater, Pennsylvania, USA

GlaxoSmithKline Biologicals, S.A. (GSK) Rixensart, Belgium

> May 20, 2020 HVTN 702 Version 4.0

On 23 January 2020, in reviewing cumulative unblinded data for HVTN 702, the NIAID HIV Vaccine Data Safety and Monitoring Board (DSMB) found that preestablished criteria for vaccine non-efficacy had been met. Accordingly, the DSMB recommended halting vaccinations. The HVTN 702 Oversight Group (OG) concurred with this DSMB recommendation and vaccinations in HVTN 702 were stopped as of 3 February 2020. The OG further determined that all HVTN 702 participants who have not yet completed their clinic visits schedules should be followed for safety for 12 months after the last vaccination they received.

Since no more participants will be vaccinated at Visit 11 (Month 18), Visit 12 (Month 18.5), whose purpose was evaluation of safety and immunogenicity following the vaccination at Visit 11, has been removed from the schedule. The visit schedule for the 12-month follow-up period for all participants remains otherwise unchanged.

HVTN 702 had an adaptive two-stage design. Stage 1 entailed following all participants for 24 months post-enrollment. Stage 2 was to be conducted if the vaccine was found to be efficacious at the end of Stage 1 and entailed following all participants for an additional 12 months to 36 months post-enrollment. Because the criteria for vaccine non-efficacy were met during Stage 1, Stage 2 of the trial will not occur.

All participants have been unblinded to their treatment assignments. Follow-up will continue in an unblinded fashion.

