Minimum 24, maximum 42 months per participant (including 6 months follow-up should a participant be diagnosed with HIV infection at their last scheduled study visit). All HIV-1–uninfected study participants will be followed for at least 24 months following enrollment unless an interim monitoring boundary is reached. If the vaccine efficacy analysis in Stage 1 (ie, months 0-24) supports continuation of the study through Stage 2 (ie, months 24-36), all HIV-1–uninfected study participants will be followed for 36 months of scheduled clinic visits. Participants who become HIV-1–infected during the study will be followed for approximately 6 months after confirmation of diagnosis.

The NIAID DSMB determined on 23 January 2020 that the interim non-efficacy boundary had been reached. Accordingly, vaccinations were stopped on 3 February 2020 and it was determined that participants should be unblinded and that follow up for HIV-uninfected participants should last 12 months following their last vaccination. At that time the last enrolled participant had passed the timepoint for the scheduled Month 6 vaccination; hence, the minimum scheduled study duration for this participant is 18 months. Some participants had already reached the 36-month maximum duration for HIV-1–uninfected participants. As indicated above, participants who become HIV-1 infected during the study will be followed for approximately 6 months after confirmation of diagnosis.

Estimated total study duration

Approximately 62 months. This includes 20 months projected for enrollment, up to 36 months follow-up for the last enrolled HIV-uninfected participant, and 6 months follow-up should the last-enrolled participant be diagnosed with HIV infection at the last [ie, Month 36] scheduled clinic visit.

Following cessation of vaccination and reduction of follow-up duration for HIV-1–uninfected participants, the estimated total study duration is reduced to approximately 44 months.

Study sponsor

DAIDS, NIAID, NIH, DHHS (Bethesda, Maryland, USA)

Study product providers

- ALVAC-HIV (vCP2438): Sanofi-Pasteur (Swiftwater, Pennsylvania, USA)
- Bivalent Subtype C gp120/MF59: GlaxoSmithKline Biologicals, S.A. (Rixensart, Belgium)

Core operations

HVTN Vaccine Leadership Group/Core Operations Center, Fred Hutchinson Cancer Research Center (FHCRC) (Seattle, Washington, USA)

Statistical and data management center (SDMC)

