Unsolicited AEs will be collected over 30 days post each vaccination visit. All collected AEs are reported to the SDMC on the appropriate CRF. Clinic staff should evaluate every AE to determine if (1) the AE meets the requirements for expedited reporting to the study sponsor (Section 12.2.3), (2) if the AE meets the criteria for immediate notification to HVTN Core (Section 12.3), and (3) if the AE is a potential immune-mediated disease that may be listed as an AESI. A sample list of AESI is provided in Appendix J. Attribution with regard to relationship to study product will be reported for all AEs.

Certain AEs will be collected and reported throughout the entire study:

- SAEs/AEs requiring expedited reporting to DAIDS (EAEs),
- AESIs
- AEs of STIs
- New chronic medical conditions (defined as a new onset or exacerbation of medical condition requiring 2 or more visits to a medical provider during a period of at least 30 days). and
- AEs leading to early participant withdrawal or early discontinuation of study product(s) administration.

In addition, site investigators are required to submit AE information in accordance with IRB/EC and any applicable RE requirements.

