HVTN 702 Open Statistical Analysis Plan for Safety, Trial Monitoring, and Vaccine Efficacy Analysis

Statistical Center for HIV/AIDS Research and Prevention
Vaccine Infectious Disease Division
Fred Hutchinson Cancer Research Center

Protocol version 3.0 (Oct. 5, 2017)
SAP Version 1.4
January 22, 2020

SAP Approval Signature Page**HVTN 702**

A Pivotal Phase 2b/3 multi-site, randomized, double-blind, placebo-controlled clinical trial to evaluate the safety and efficacy of ALVAC-HIV (vCP2438) and Bivalent Subtype C gp120/MF59 in preventing HIV-1 infection in adults in South Africa

I have read this Statistical Analysis Plan and approve its contents.

[name]
Principal Staff Scientist
Vaccine and Infectious Disease Division
Fred Hutchinson Cancer Research Center

Date

F. [name]
Senior Staff Scientist
Vaccine and Infectious Disease Division
Fred Hutchinson Cancer Research Center

Date

SAP Modification History

The version history of, and modifications to, this statistical analysis plan are described below.

Date: September 7, 2016

Protocol version: 1.0

SAP version: 1.0

Date: August 28, 2018

Protocol version: 3.0 (October 5, 2017)

SAP version: 1.1

Modifications:

- 1) Section 2: Changed maximum follow-up from 36 months to 42 months in accordance with Protocol Version 3.0.
- 2) Section 3: clarified that the Week 26 at-risk cohort is defined based on ELISA testing results for uninfected participants and based on PCR testing results (if available) for infected participants. In the event that the PCR testing result is not available at visit 6 (Week 26) for an infected participant, the mid-point between the last RNA-negative and first RNA-positive date will be used to determine whether the participant is in the Week 26 at-risk cohort. In the event that the PCR testing result is not available at any visit for an infected participant, e.g., during an interim analyses when some participants might be recently diagnosed as HIV-infection with no retrospective testings performed yet, the participant will be included in the cohort only if his/her latest negative ELISA test is from a visit at or after visit 6.
- 3) Section 4.1: Clarified that the date of diagnosis will be used as the primary event-date for time-to-event analyses related to VE and added text for the secondary analyses that use other definitions for the HIV event date.
- 4) Section 4.2: Added sensitivity analyses of VE using EPIT.

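### SAP Section 9 cuts every safety analysis at unblinding and was not reconciled with protocol 4.0, which continues unblinded safety follow-up to 12 months after the last vaccination

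*SAP*

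**What the plan says.** **SAP.** Section 9 opens its safety analysis with a data cut: "All analyses will only use samples and data gathered prior to study unblinding". The same sentence opens Section 10 on efficacy. SAP 7.1 defines the long-term part of primary endpoint 2 as SAEs, AESIs and new chronic conditions "occurring at any time throughout the study", plus AEs leading to withdrawal or to stopping study product over the whole study. Section 9 itself plans a chronic-conditions listing with the same whole-study scope. Section 6 says that, without Stage 2, the final analysis waits for the last enrolled participant's final visit. The SAP is version 1.4, dated "January 22, 2020", and names protocol 3.0 as the version it serves.

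**Protocol.** The version in force is headed "May 20, 2020 HVTN 702 Version 4.0". Its boxed opening text reports the DSMB finding of 23 January 2020, the stop to vaccinations as of 3 February 2020, and the unblinding of all participants. Those who had not finished their visit schedule "should be followed for safety for 12 months after the last vaccination they received". Section 9.4.1 keeps AE assessment at every post-unblinding visit. Section 12.2.2 says: "Certain AEs will be collected and reported throughout the entire study"; the list covers SAEs, AESIs, new chronic conditions and AEs leading to withdrawal or product discontinuation. Section 5.1 gives primary endpoint 2 the same whole-study scope. Section 6.9.3, on safety analysis, sets no cut at unblinding and describes no post-unblinding analysis. Section 6.9.5.1 does describe an analysis of pre- and post-unblinding data, but only for HIV acquisition.

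**The concern.** A primary endpoint that runs to the end of the study is paired with an analysis rule that stops at unblinding. Under protocol 4.0 the gap between those two points is follow-up that the protocol continues for safety. The final analysis would wait for the last visits to be completed, and Section 9 would then bar what those visits collected.

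The events at stake are late ones: SAEs, AESIs (which include potential immune-mediated disorders), new chronic conditions and AEs leading to withdrawal. The missing follow-up is concentrated in the most recently vaccinated participants. DSMB review of safety data by group ended on 23 January 2020 (Protocol 12.4.3), so no other planned analysis by arm covers the period.

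**Working it through.** The finding is a conflict between texts; arithmetic gives its size.

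**1. The plan's own figure.** Protocol Section 3 (Duration per participant) says that when vaccinations stopped, the last enrollee had passed the Month 6 vaccination timepoint, and that "the minimum scheduled study duration for this participant is 18 months". Month 6 + 12 months = 18 months, so the figure reproduces.

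**2. When unblinding happened.** The documents give no date. It is assumed to lie between 3 February 2020 (vaccination stop) and 20 May 2020 (protocol 4.0, which states that all participants have been unblinded). These dates are 107 days apart.

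**3. Share of the 12-month window excluded.** For a participant last vaccinated on date V:

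excluded share = 1 − (days from V to unblinding) / (days in the 12 months after V), with a minimum of 0.

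For V = 3 February 2020 the window is 366 days. Unblinding on 3 February gives 1 − 0/366 = 100%. Unblinding on 20 May gives 1 − 107/366 = 71%. The other vaccination dates below are illustrative assumptions.

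| Last vaccination | Days kept | Days in window | Excluded |
|---|---|---|---|
| 3 Feb 2020 (last possible) | 0 to 107 | 366 | 71–100% |
| 3 Nov 2019 | 92 to 199 | 366 | 46–75% |
| 3 Aug 2019 | 184 to 291 | 366 | 20–50% |
| 20 May 2019 | 259 to 366 | 366 | 0–29% |
| 3 Feb 2019 or earlier | all | 365 | 0% |

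**4. The last enrollee's 18 months.** At least 6 months had passed by 3 February 2020. Unblinding on that day excludes at most 12/18 = 67%. Unblinding on 20 May adds about 3.5 months, so at least 9.5 are kept and at most 8.5/18 = 47% is excluded. These are upper limits, because the participant was already past Month 6.

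**5. Which endpoints lose data.**
- Solicited reactogenicity covers 3 days after each dose. It is complete unless unblinding fell within 3 days of the last dose.
- General unsolicited AEs are collected for 30 days after each dose. For the last possible dose that window closed on 4 March 2020, so it is complete if unblinding came on or after that date.
- AEs leading to product discontinuation lose essentially nothing, because dosing had stopped.
- SAEs, AESIs, new chronic conditions and AEs leading to withdrawal lose everything after unblinding.

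**6. The formal comparisons.** SAP Section 9 applies Barnard's test to four aggregates: any reactogenicity, any related AE, and each of these at grade 3 or higher. By step 5, these rest almost entirely on data from before unblinding.

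**The case against.** The strongest reply is about timing. SAP 1.4 predates the DSMB finding by one day. Under protocol 3.0, which it serves, blinding was to last through Stages 1 and 2, so the sentence would have excluded essentially no scheduled follow-up. It was not a decision to discard safety data. That stands as the explanation, but it does not close the gap. SAP Section 5 already foresaw an early non-efficacy stop with possible continued follow-up, protocol 4.0 did not address the point for safety, and no later SAP is among the documents.

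Three stronger readings are tempting and are not supported:

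- *The whole 12-month safety follow-up is discarded.* Only the part after unblinding is. Some participants had already reached 36 months.
- *Most of the last enrollee's follow-up is lost.* That depends on an unblinding date the documents do not give. At the later end of the assumed range the loss is under half.
- *The formal between-arm safety tests are compromised.* They rest almost entirely on 3-day and 30-day data. SAEs, AESIs and chronic conditions are planned as listings, outside those tests.

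It is also fair that the events are not lost to the study: collection, expedited reporting and routine review by the safety review team continue under Protocol Section 12. And a pre-unblinding cut has a real merit. Sites assign relatedness, and after unblinding they know the arm. That supports keeping the cut for the formal comparisons of related AEs. It does not support omitting late events from every table and listing.

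**Conclusion.** The concern holds as a failure to reconcile the SAP with protocol 4.0. Followed literally, Section 9 does not fully analyse primary endpoint 2, and it contradicts SAP 7.1 and its own chronic-conditions listing. The loss falls on four kinds of late event and mainly on recent vaccinees, with the sizes worked out above. Those sizes rest on the assumed range for unblinding and, for the intermediate rows of the table, on illustrative vaccination dates. The textual conflict rests on neither. The number of events affected cannot be estimated from the documents.

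**What to change.** Amend SAP Section 9 for protocol 4.0 before the final safety analysis:

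- Summarise and list SAEs, AESIs, new chronic conditions and AEs leading to withdrawal or product discontinuation by arm over all follow-up.
- Show the periods before and after unblinding separately, because later reporting is open-label.
- State the unblinding date.
- Keep the pre-unblinding cut for reactogenicity and for the formal Barnard comparisons of related AEs.

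At the same time, reconcile the identical sentence opening SAP Section 10 with primary endpoint 3, which counts HIV infections over the whole of participant follow-up, and with the analysis in Protocol 6.9.5.1.

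The cost is a short amendment and one extra set of tabulations. The downside is that late events carry open-label reporting bias; the split makes this visible but does not remove it.
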